2.10	PD and PK/PD analyses.....	20
2.11	Biomarkers.....	20
2.12	Other exploratory analyses	20
2.13	Interim analysis.....	21
3	Sample size calculation	21
4	Change to protocol specified analyses	21
5	Appendix	21
5.1	Imputation rules	21
5.1.1	AE date imputation	21
5.1.2	Concomitant medication date imputation	23
5.2	Calculation of Dermatology Life Quality Index (DLQI)	24
5.3	Calculation of Brief Index of Sexual Functioning for men and woman (BISF-M and BISF-W)	26
5.4	SAS code	27
6	Reference.....	28

List of abbreviations

AE	Adverse event
ATC	Anatomical Therapeutic Classification
AUC	Area under the curve
BISF-m	Brief Index of Sexual Functioning for men
BISF-w	Brief Index of Sexual Functioning for woman
BMI	Body mass index
BSA	Body surface area
CI	Confidence Interval
CSR	Clinical Study Report
CT	Computerized tomography
DBL	Database lock
DLQI	Dermatology Life Quality Index
ECG	Electrocardiogram
EOE	End of Extension
EOT	End of Treatment
FAS	Full Analysis Set
i	Intervention
IGA	Investigator's Global Assessment
IS	Included Set
LOCF	Last Observation Carried Forward
LPLV	Last Patient Last Visit
MedDRA	Medical Dictionary for Regulatory Activities
MRI	Magnetic resonance imaging
NovDTD	Novartis Drug and Therapy Dictionary
p	Psychosocial
PASI	Psoriasis Area and Severity Index
PFS	Pre-filled syringe
PLS	Product Lifecycle Service
PPS	Per Protocol Set
proSPI	Professionally-administrated Simplified Psoriasis Index
PT	Preferred term
QFT	QuantIFERON®-TB
ROC	Receiver Operating Characteristic
s	Severity
SAE	Serious adverse event
SAF	Safety Analysis Set
SAP	Statistical Analysis Plan
saPASI	Self-administrated Psoriasis Area and Severity Index
saSPI	Self-administrated Simplified Psoriasis Index
SD	Standard deviation
SE	Standard error
SOC	System organ class

SPI Simplified Psoriasis Index
TEAE Treatment-emergent adverse events

1 Introduction

The purpose of this Statistical Analysis Plan (SAP) is to describe the statistical methods planned in Section 9 of the study protocol version 5 of phase IIIb clinical trial CAIN457AFR01 along with any additional analyses, specifications or deviations from this protocol planned before database lock (DBL). Determination of sample size is specified in [Section 3](#).

This document is written in the future tense. It will be reviewed and updated (including conversion to past tense) for entry into the clinical study report after the analysis has taken place.

1.1 Study design

This is an open-label multicenter, single arm study in 120 patients with moderate to severe psoriasis. There will be no randomization nor interim analysis for this study.

[figure not shown]
The study consists of five epochs:

- Screening to occur between day -28 and day -7
- Treatment
 - Treatment period 1
 - Treatment period 2
- Extension treatment period
- Follow-up

There will be an initial induction phase (5 weekly injections) before switching to monthly injections until Week 16. The patient will continue with monthly injections until Week 48 in case of a favorable response to treatment at Week 16. Patients who are deemed to be benefiting from the study drug after 48 weeks of treatment could be continuously treated until 3 November 2016 or until commercialization of Cosentyx[®] in France, whichever occurs first.

An illustration of the study design is depicted in [Figure 1.1](#).

Figure 1-1 Study design

1.2 Study objectives and endpoints

1.2.1 Primary objective

The primary objective is to evaluate the benefit of secukinumab on the severity of psoriasis based on the Simplified Psoriasis Index (SPI). This index comprises 3 components: severity (s), psychosocial (p), and intervention (i). All components of SPI will be evaluated by both the physician (proSPI) and the patient (self-assessed: saSPI). Only the severity component will be evaluated for the primary objective, i.e. both proSPI (s) and saSPI (s).

1.2.2 Secondary objectives

Key secondary objectives are:

- ✓ to assess Psoriasis Area and Severity Index (PASI) weekly from week 0 to 4 then every 4 to 8 weeks until Week 56
- ✓ to evaluate correlation between PASI and proSPI (s)

Other secondary objectives include:

- ✓ to assess proSPI (s, p and i) over time (weekly from Week 0 to Week 4 then every 4 to 8 weeks until Week 56).
- ✓ to assess saSPI (s, p and i) over time (weekly from Week 0 to Week 4 then every 4 to 8 weeks until Week 56).
- ✓ to assess Dermatology Life Quality Index (DLQI) over time (weekly from Week 0 to Week 4 then every 4 to 8 weeks until Week 56).
- ✓ to assess self-administered PASI (saPASI) (weekly from Week 0 to Week 4 then every 4 to 8 weeks until Week 56).
- ✓ to assess pain, itching, and scaling using the Psoriasis Symptom Diary questionnaire over time (weekly from Week 0 to Week 4 then every 4 to 8 weeks until Week 56).

- to evaluate correlation between proSPI (for each component separately: s, p, i) and DLQI
- to evaluate correlation between proSPI (p, i separately) and PASI
- to evaluate safety during the treatment period (until the Week 52) and during the extension treatment period (after the Week 52)

1.2.3 Exploratory objectives

- to evaluate correlation between saSPI (s, p, i separately) and DLQI.
- to evaluate correlation between proSPI (s, p separately) and saSPI (s, p separately).
- to evaluate correlation between saSPI (s) and PASI.
- to evaluate the ability of SPI to discriminate between responders and non-responders based on PASI response.
- to explore sexual dysfunction using the Brief Index of Sexual Functioning for men/woman (BISF-m or BISF-w) questionnaire in a subset of subjects willing to complete sexual function questionnaire.

2 Statistical methods

2.1 Data analysis general information

The analysis will be performed by Novartis. The statistical software used for the analyses will be SAS version 9.4 or later.

Descriptive statistics for continuous variables in the study will include the number of observations, mean, standard deviation (SD), median, minimum, and maximum. The following number of decimal places will be used: mean, and median, values to 1 more decimal place than the raw data; minimum and maximum to the same number of decimal places as the raw data and SD to 2 more decimal places than the raw data.

For categorical variables frequency and percentage will be presented for non-missing data.

If appropriate, 95% Confidence Intervals (CIs) will be presented along with p-values.

Unless otherwise specified, all statistical tests will be two-sided and will use the 5% level of significance.

All data will be listed by patient unless stated otherwise.

2.1.1 General definitions

2.1.1.1 Study treatment

The investigational drug, secukinumab, is to be injected subcutaneously and will be provided by Novartis in pre-filled syringes (PFS) of 150 mg. Two injections will therefore be necessary to obtain the required dosage of 300 mg.

2.1.1.2 Study day

The day of first administration of the treatment will be considered as study day 1. All other study day will be labeled relative to study day 1.

The day for a particular event on or after the study day 1 will be calculated as:

$$\text{date of event} - \text{date of first dose} + 1$$

The day before study day 1 will be calculated as:

$$\text{date of event} - \text{date of first dose}$$

2.1.1.3 Baseline and post-Baseline

Baseline data will be defined as the last available non-missing data collected prior to the first study treatment administration. Data collected after first dose of study treatment will be considered as post-Baseline data.

Change from Baseline will only be summarized for patients with both Baseline and post-Baseline unless stated otherwise, and it will be calculated as:

$$\text{post-Baseline value} - \text{Baseline value}$$

Correspondingly, percentage change will be calculated as:

$$100 * (\text{post-Baseline value} - \text{Baseline value}) / \text{Baseline value}$$

2.1.1.4 Visit windows

Visit windows will be used for the data that is summarized by visit. They are based on the study evaluation schedule and comprise a set of days around the nominal visit day. For any assessment, there are the protocol defined scheduled visits around which visit windows were created to cover the complete range of days within the study. The visit windows in this study are shown in [Table 2-1](#). In this table, the days are counted since the first dose of study treatment. These visit windows apply to measurements taken at every visit. When visit windows are used, all visits (except follow up visits) will be re-aligned, i.e., they will be mapped into one of the visit windows. E.g., if the Week 4 visit of a subject is delayed and occurs on Day 46 instead of on Day 29, say, it will be re-aligned to visit window Week 8. If two visits fall into one window then the visit closest to target scheduled day will be analysed for that visit. Follow up visits will not be re-aligned.

Table 2-1 Assessment windows for scheduled visits

Visit	Week	Scheduled day	Visit Window
Baseline	0	1	-28 days to day 1
Visit 2	1	8	Day 2-11
Visit 3	2	15	Day 12-18
Visit 4	3	22	Day 19-25
Visit 5	4	29	Day 26-43
Visit 6	8	57	Day 44-71
Visit 7	12	85	Day 72-99

Visit	Week	Scheduled day	Visit Window
Visit 8	16	113	Day 100-141
Visit 9	24	169	Day 142-197
Visit 10	32	225	Day 198-253
Visit 11	40	281	Day 254-309
Visit 12	48	337	Day 310-351
Visit 13	52	365	Day 352-379
Extension 1	56	393	Day 380-421
Extension 2	64	449	Day 422-477
Extension 3	72	505	Day 478-533
Follow-up	80	561	≥ Day 534

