2.1.1.5 Follow up visit

Efficacy data collected at follow up visits will not be summarized.

Efficacy data collected at follow up visits will be listed.

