2.1.1.6 Unscheduled visit

All safety and exposure to study treatment data collected at unscheduled visits will be summarized.

Efficacy data collected at unscheduled visits will be visit windowed as per section 2.1.1.4 and will be presented in the same manner as scheduled visits.

All data collected at unscheduled visits will be listed.

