2.6.1 Key secondary endpoint

The key secondary variables are:

- absolute PASI score values at each post-Baseline visit until end of study
- the correlation coefficient between PASI and proSPI (s) at each post-Baseline visit

The key secondary endpoints analyses will be based on the FAS (observed data only).

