2.13 Interim analysis

No interim analysis is planned in this study.

3 Sample size calculation

The samples size calculation is based on the primary objective of the study which is to evaluate the benefit of secukinumab on the severity and psychosocial burden of psoriasis based on SPI change at Week 16 compared to Baseline in patients suffering from moderate to severe plaque psoriasis.

A similar study by Chularojanamontri et al. (2013) showed that it is possible to detect responsiveness and a minimum clinically important difference (an absolute change of 5 and 7 for proSPI (s) and saSPI (s), respectively) derived from PASI changes with 100 patients. The study showed a SD of 7.35 and 10.35 in change from Baseline at Week 10 in proSPI (s) and saSPI (s) respectively. As the SD at Week 16 is expected to be higher, conservative SD estimates of 14 and 19 will be assumed for change at Week 16 for proSPI (s) and saSPI (s) respectively.

Based on an analysis of paired differences, in order to have at least 90% power to detect a significant clinical difference for each index at the 2.5% level (2-sided), it can be estimated that a sample size of 100 evaluable patients would be sufficient.

Taking into account an anticipated drop-out of 20 patients, 120 patients will need to be included in the study.

4 Change to protocol specified analyses

Any objectives to be assessed until Week 56 will be changed to until end of study.

5 Appendix

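### As written, the Follow-up window in Table 2-1 (Day 534 or later) can receive only visits that are not follow-up visits, and the SAP does not say how those visits are summarised

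*SAP*

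**What the plan says.** Section 2.1.1.4 sets the mapping rule: "When visit windows are used, all visits (except follow up visits) will be re-aligned, i.e., they will be mapped into one of the visit windows". It closes the paragraph by repeating the exemption: "Follow up visits will not be re-aligned". It also says that the "visit windows were created to cover the complete range of days within the study", and that when two visits fall in one window, the one nearer the scheduled day is used.

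The last two rows of Table 2-1 are:

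- Extension 3: Week 72, scheduled Day 505, window Day 478-533.
- Follow-up: Week 80, scheduled Day 561, window Day 534 or later, with no upper limit.

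Four other places bear on the point:

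- Section 2.1.1.5: "Efficacy data collected at follow up visits will not be summarized". The data are listed.
- Section 2.1.1.6: "Efficacy data collected at unscheduled visits will be visit windowed as per section 2.1.1.4", and then presented as scheduled visits are.
- Section 1.1: patients judged to benefit after 48 weeks "could be continuously treated until 3 November 2016 or until commercialization of Cosentyx" in France, whichever comes first. No final week is fixed.
- Sections 2.6.1 and 4: the key secondary variable is "absolute PASI score values at each post-Baseline visit until end of study", and "Any objectives to be assessed until Week 56 will be changed to until end of study".

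**The concern.** The table row and the text around it do not fit together. A day window exists to assign visits, yet the visits this row is named after are never assigned by day. Every other visit from Day 534 onward has no other window to go to.

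Three things are at stake:

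- **Labelling.** Extension or unscheduled visits would be reported as Follow-up.
- **Late efficacy data.** Depending on how section 2.1.1.5 is read, these data could be left out of the by-visit summaries. Section 4 deliberately moved the horizon from Week 56 to the end of the study.
- **By-visit safety tables.** Laboratory and vital-sign results are summarised by visit (sections 2.8.3 and 2.8.4.2). Visits made during extension treatment could sit in one row with true follow-up visits, so the change from Baseline in that row would describe neither group cleanly.

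**Working it through.** **1. Reproduce the window boundary.** Scheduled day = 7 × week + 1. The upper limit of a window is the midpoint of adjacent scheduled days, rounded down.

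- Week 72: 7 × 72 + 1 = 505. Week 80: 7 × 80 + 1 = 561.
- (505 + 561) / 2 = 533, so Extension 3 ends on Day 533 and the next window starts on Day 534.

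All 16 post-Baseline windows in Table 2-1 follow from this rule. The boundary is correct arithmetic; the defect lies in what the last row is applied to.

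**2. Which visits can enter the last row.**

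- True follow-up visits: exempt from mapping under section 2.1.1.4, so never placed by day.
- Scheduled extension visits: mapped by day. Day 505 and Day 533 go to Week 72; Day 534 goes to Follow-up.
- Unscheduled visits: efficacy is mapped by day under section 2.1.1.6, so from Day 534 they also go to Follow-up.

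The row therefore receives only non-follow-up visits. For a Week 72 visit to be caught it must be at least 534 − 505 = 29 days late.

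**3. What the label does.** The SAP's own example moves a Week 4 visit held on Day 46 to Week 8, so a re-aligned visit takes the name of its new window. The Follow-up window is open-ended with target Day 561, and only the closest visit is kept. For illustration, a patient with non-follow-up visits on Days 561 and 617 (561 + 56) would keep Day 561; Day 617 would leave the by-visit summary.

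**4. Can a patient be on treatment at Day 534?** Day 534 is 533 days after first dose (533 / 7 = 76.1 weeks). The latest possible treatment date in section 1.1 is 3 November 2016.

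- 3 November 2016 − 533 days = 20 May 2015.
- For Day 561: 3 November 2016 − 560 days = 23 April 2015.

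A patient first dosed on or before 20 May 2015, and treated up to the calendar limit, reaches Day 534 during extension treatment. Earlier commercialization would move that cut-off earlier. The SAP gives neither enrolment dates nor a commercialization date, so the count runs from zero to all patients dosed early enough who continued.

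**5. Are the efficacy data summarised?** There are two readings of section 2.1.1.5:

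- *By the visit at which data were collected.* Extension and unscheduled visits are not follow-up visits, so their data are summarised, but under the name Follow-up and one visit per patient.
- *By assigned window.* A visit mapped to Follow-up counts as a follow-up visit, so its efficacy is listed only. This conflicts with sections 2.6.1 and 4.

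The SAP does not choose between them.

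**The case against.** A reader might infer that on-treatment efficacy after Day 533 is dropped from every summary. The SAP does not support that as a fact. Section 2.1.1.5 turns on where the data were collected, which read literally means actual follow-up visits. Sections 2.1.1.6 and 2.6.1 point towards summarising the data. The loss follows only if the assigned label defines the visit, a step the SAP never states. Even then only efficacy summaries lose data; the listings remain, and section 2.1.1.5 does not restrict safety summaries.

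It can also be said that no affected visit is shown to exist. Table 2-1 schedules no extension visit after Week 72. The category above 72 weeks in section 2.4.1 does not prove later dosing, because exposure is counted to the end-of-study date and the Extension 3 window itself runs to about 76 weeks. Section 5.3 cites an email dated 09/01/2017, which on either date format is after 3 November 2016. The authors may therefore have known that three extension visits covered the data. That is a fair inference, though not proof.

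Finally, moving a late visit into the next window is the SAP's ordinary rule, and the late summaries are descriptive, on observed data, in a single-arm study.

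These arguments limit the consequence. They do not remove the conflict between the row and the text, or the mislabelling on either reading.

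**Conclusion.** The point holds as an internal inconsistency that should be corrected before database lock. As written, the Follow-up window can receive only non-follow-up visits; it renames them and keeps one per patient. In the by-visit laboratory and vital-sign tables they would share a row with true follow-up visits. Omission of their efficacy from by-visit summaries is conditional on reading the assigned label as defining a follow-up visit.

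The size cannot be computed from the SAP and may be zero. It depends on whether any Week 72 visit was 29 or more days late, whether any unscheduled visit fell on or after Day 534, and whether any extension visit took place beyond Week 72. The co-primary Week 16 analysis (window Day 100-141) is unaffected.

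**What to change.** In section 2.1.1.4 and Table 2-1:

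- Identify Follow-up by the nominal eCRF visit only, and remove its day range from the mapping.
- Assign any non-follow-up visit on or after Day 534 to a separate late-extension window or windows. If such data exist, 56-day steps would continue the existing spacing: Day 534-589 around Day 561, then Day 590-645 around Day 617. These are analysis windows and add no visit to the schedule.
- State that efficacy in these windows is summarised like the other extension visits, and that section 2.1.1.5 applies only to nominal follow-up visits.
- Keep Follow-up as a separate row in the safety tables.

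The cost is SAP wording and, if needed, a few table rows. The downside is small numbers in any late rows. If the data contain no such visits, a sentence saying so is enough once the Follow-up day range has been removed.

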2.5.3 Handling of missing values/censoring/discontinuations

Missing data will be imputed using Last Observation Carried Forward (LOCF) method. This approach will consist of replacing the missing Week 16 assessment by the last non-missing assessment value.

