2.5.4 Supportive/sensitivity analyses

To assess for robustness of the results, the same analysis as specified in [Section 2.5.2](#) will be repeated for the FAS (on observed data).

The primary analysis for the two co-primary endpoints will be also be performed on the PPS.

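### The SAP leaves open whether an SPI severity score taken at a follow-up visit inside the Week 16 window may be used, and its closest-visit rule can pass over an observed score (minor)

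*SAP*

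**What the plan says.** **Windows.** SAP 2.1.1.4 maps visits to analysis windows with one exception: "When visit windows are used, all visits (except follow up visits) will be re-aligned", and it adds "Follow up visits will not be re-aligned". In Table 2-1 the Week 16 window is Day 100-141 with target Day 113. The table's single follow-up row is Week 80, Day 561.

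**Follow-up data.** SAP 2.1.1.5 states "Efficacy data collected at follow up visits will not be summarized" and also "Efficacy data collected at follow up visits will be listed". The plan thus expects efficacy data at follow-up but confines them to listings.

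**Unscheduled visits.** SAP 2.1.1.6 treats these differently: "Efficacy data collected at unscheduled visits will be visit windowed as per section 2.1.1.4".

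**Two visits in one window.** SAP 2.1.1.4: "If two visits fall into one window then the visit closest to target scheduled day will be analysed for that visit". The choice is made between visits, not between scores.

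**Missing Week 16.** SAP 2.5.3 applies LOCF by "replacing the missing Week 16 assessment by the last non-missing assessment value". It does not limit which visits can supply the value.

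**Supportive analyses.** SAP 2.5.4 repeats the co-primary analysis on observed data in the FAS and on the PPS.

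**The concern.** Suppose a patient stops treatment early and has SPI (s) scored at a follow-up visit on, say, Day 113. Under 2.1.1.4 and 2.1.1.5 that score is not a Week 16 record, so Week 16 counts as missing. The likely reading of 2.5.3 then puts an earlier on-treatment score in its place. Had the same visit been labelled unscheduled, its score would have entered the window.

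What is at stake is the estimated mean change in the two co-primary endpoints. If disease had worsened off drug, the LOCF mean would overstate the benefit; if the patient had improved on another therapy, it would understate it. The supportive analyses cannot reveal either. The observed-data run drops the patient, and the PPS run repeats the primary method.

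The rule is also not fully determined. Because 2.5.3 does not restrict the LOCF source, a literal programmer could carry the follow-up score itself. Two programmers could therefore build different co-primary datasets from the same text.

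A second, independent weakness is the closest-visit rule. If the visit nearest Day 113 lacks saSPI (s) and another in-window visit has it, the rule selects the visit without the score.

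**Working it through.** **1. The plan's own figure.** SAP section 3 uses differences of 5 (proSPI (s)) and 7 (saSPI (s)), SDs of 14 and 19, two-sided 2.5% and at least 90% power. A paired t-test by noncentral t needs 100 patients for proSPI (s) (power at 100: 90.05%) and 94 for saSPI (s) (power at 100: 91.9%). With 20 drop-outs, 100/(1 − 20/120) = 120. The stated 100 and 120 reproduce, and this point does not touch them.

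**2. Could follow-up fall in the Week 16 window?** Table 2-1 puts follow-up at Day 561 and the last extension visit at Day 505: 561 − 505 = 56 days. *Assumption:* the same gap applies to early leavers.
- Earliest last visit: 100 − 56 = Day 44.
- Latest last visit: 141 − 56 = Day 85.
- Week 8 leaver: 57 + 56 = Day 113, the Week 16 target.
- Week 12 leaver: 85 + 56 = Day 141, the last day of the window, so a one-day delay takes the visit outside.

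The situation is possible, mainly for patients whose last visit is around Week 8.

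**3. Size.** If k of 120 FAS patients have an in-window value that differs by L points from the value carried forward, the mean change shifts by k × L/120. Neither k nor L is in the SAP.

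| k (assumed) | L (assumed) | Shift in mean change |
|---|---|---|
| 5 | 5 | 0.21 |
| 10 | 5 | 0.42 |
| 10 | 10 | 0.83 |
| 20 (every anticipated drop-out) | 5 | 0.83 |
| 20 | 10 | 1.67 |

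The rows with k = 20 are an extreme bound.

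**4. Against the test.** At the planning SDs, the standard error is 14/√120 = 1.28 for proSPI (s) and 19/√120 = 1.73 for saSPI (s). A shift of 0.83 is below one standard error for both. If the mean changes equalled the planning differences:
- proSPI (s): t falls from 5/1.28 = 3.9 to (5 − 0.83)/1.28 = 3.3.
- saSPI (s): t falls from 7/1.73 = 4.0 to (7 − 0.83)/1.73 = 3.6.

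Both remain well beyond the two-sided 2.5% critical value of about 2.27.

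**5. Closest-visit rule.** No arithmetic is needed. SAP 2.1.1.6 brings unscheduled visits into the same windows, so two visits in one window are foreseeable. The rule in 2.1.1.4 compares visit dates and ignores whether the score is present. By contrast, the Baseline definition in 2.1.1.3 does require a non-missing value.

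**The case against.** The strongest reply is that keeping post-treatment scores out of an on-treatment analysis is a coherent choice of what to estimate. That stands, and it is why the primary analysis should stay. What is missing is a statement of the choice and a check on its effect.

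The factual basis is also thin. The SAP does not say when an early leaver attends follow-up or that SPI is scored there; these details may be in the protocol. The 56-day gap is read from a single row of Table 2-1. It is also the spacing of the visits from Week 16 to Week 48 and of the extension visits, so it may be no more than the next slot on the grid. This stands too, and the point has to remain conditional.

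A reader might infer more than the text supports:
- *That follow-up scores are barred from the primary analysis.* The SAP says they are not re-aligned and not summarised. It does not exclude them as a LOCF source.
- *That everyone leaving between Day 44 and Day 85 is affected.* The patient must also attend, attend on time and have SPI scored.
- *That the result is biased in favour of the drug.* A leaver may have begun another psoriasis therapy, so the direction is open.

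On the closest-visit rule, it can be said that LOCF may still recover a non-missing in-window score from before the selected visit. That is a partial answer. On the ordinary meaning of LOCF a later in-window score is not recovered, and the observed-data run has no LOCF to fall back on.

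**Conclusion.** The point holds in a limited, conditional form. The SAP keeps follow-up visits out of the Week 16 window, does not say whether their scores may feed LOCF, and has no analysis that would show the effect. If such scores exist, the likely reading replaces an observation with an earlier on-treatment value.

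The effect on the mean change is about 0.2 to 0.8 points for 5 to 10 patients differing by 5 to 10 points each. All of these inputs are assumed, as are the 56-day gap and a FAS of 120. For scale, the clinically important differences in section 3 are 5 and 7. The sign is unknown, and the co-primary test decision is not expected to change.

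The closest-visit weakness needs no assumption about follow-up timing and should be corrected in any case. Overall priority: minor.

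**What to change.** 1. **SAP 2.1.1.4:** for each score, select the non-missing value closest to the target day within the window, instead of the closest visit.
2. **SAP 2.5.3:** state that the primary analysis is on-treatment and uses no follow-up value as a Week 16 record or as a LOCF source.
3. **SAP 2.5.4:** add one sensitivity analysis of both co-primary endpoints. Week 16 is the non-missing SPI (s) value closest to Day 113 within Day 100-141, whether the visit was scheduled, unscheduled or follow-up. LOCF applies only if there is no such value.

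The cost is a few sentences before database lock and one more run of the same test, with no new data. The downside is that the added run mixes a few off-drug scores into Week 16. It therefore answers a treatment-policy question beside the primary one and should be labelled that way.
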